3.2 Clinical Event Description and CEC Adjudication

Three types of events are defined in the sections below. All clinical events will be adjudicated by a Clinical Events Committee (CEC) consisting of a blinded panel of independent experts. Once the CEC adjudicates the Clinical Events, and per defined criteria in section 3.2.2, all Type I ST episodes will be classified as either False Positive or True Positive events. In addition, any Clinical Event that was not associated with a Type I ST episode detection will be classified as either False Negative or True Negative.

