3.2.1 Clinical Event Committee

The CEC will include at a minimum, 2 interventional cardiologists and 2 electrophysiologists. Physicians on the CEC will not participate in the study as investigators and when reviewing events will be blinded to any patient or site information. The purpose of the CEC is to adjudicate all clinical events. Specifically:

- Classify clinical events as either an Acute Coronary Syndrome (ACS) Event, a Precursor Event, or a Non Event. Non Events will be further classified as either a Transient Ischemic Event or a Non Ischemic Event. Review all deaths, and adverse events associated with diagnostic testing or procedures performed as a result of a Type I ST Episode Detection and determine relationship to system and/or procedure.
- Review all baseline surface ECGs to determine the presence or absence of any conduction abnormality.
- Review all complications and all cardiovascular related adverse events

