3.2.2 Clinical Events

ACS Events

An ACS event is defined as any of the following:

- Death due to a myocardial infarction
- A new Q-wave myocardial infarction on 12-lead ECG
- ST elevation myocardial infarction
- Biomarker evidence of acute myocardial damage*
- Evidence of new plaque rupture by invasive testing (i.e., IVUS) as adjudicated by the blinded Clinical Events Committee
- The presence of TIMI myocardial perfusion grade 0 or 1 consistent with acute injury of the myocardium from embolization
- New surface ECG ST depression or elevation treated with thrombolytic medication

Statistical Analysis Plan

- New surface ECG ST depression or elevation with new or progressive flow-limiting ischemia proven by non-invasive or invasive testing.
- Angiographic stenosis $\geq 70\%$ adjudicated by the blinded Clinical Events Committee as flow-limiting.
- An event that leads to a clinically warranted percutaneous coronary intervention (PCI) or revascularization as determined by the blinded Clinical Events Committee. Clinically warranted is defined as:
 - Angiographically visualized stenosis $\geq 70\%$ correlating with the vascular distribution in which a 12-lead surface ECG documents changes consistent with ischemia or injury in 2 or more contiguous leads
 - Angiographically visualized stenosis $\geq 70\%$ correlating with a vascular distribution shown to have ongoing ischemia by non-invasive stress testing
 - New or progressive angiographically visualized stenosis $\geq 70\%$ correlated with new or progressive anginal symptoms

*NOTE: It is recommended that the “Universal Definition of Myocardial Infarction” proposed by the Joint ESC/ACCF/AHA/WHF in 2007 be used to determine myocardial damage.

Precursor Events

A precursor event is defined as clinical symptoms of an impending ACS event followed by an ACS event within 10 days. Precursor events alone do not meet the ACS event criteria. Multiple precursor events may precede a single ACS. All precursor events will be adjudicated by the Clinical Event Committee (CEC). Symptoms identified as precursors will be grouped with the subsequent ACS event and counted as a single event. Individual precursor events will not be included in the statistical endpoint analysis.

Non Events

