Non Events are defined as any clinical event that does not meet the criteria of an ACS Event or a Precursor Event. These events will be adjudicated by the CEC and will be further classified as either Transient Ischemic Events or as Non Ischemic Events.

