3.2.3 Classification of Events

True Positive (TP): A Type I ST episode detection that occurs up to 72 hours prior to an ACS Event.

False Positive (FP): A Type I ST episode detection that occurs more than 72 hours prior to an ACS Event or that occurs in the absence of a true ACS Event.

True Negative (TN): Absence of a Type I ST episode detection during a Non Event.

False Negative (FN): Absence of a Type I ST episode detection within 72 hours prior to an ACS Event.

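### A death the CEC cannot attribute has no class of its own: it stays out of the sensitivity denominator and, if counted as a clinical event without an alarm, is scored as a True Negative

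*Protocol*

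**What the plan says.** The relevant sections read the same in the Protocol and the SAP.

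- **CEC classes (3.2.1).** The committee is to "Classify clinical events as either an Acute Coronary Syndrome (ACS) Event, a Precursor Event, or a Non Event". It also reviews all deaths, but the task attached to that review is to assess them "and determine relationship to system and/or procedure".
- **ACS criteria (3.2.2).** The only criterion that names a fatal event is "Death due to a myocardial infarction". The others rest on ECG, biomarker, angiographic, invasive or stress-test findings, or on treatment given.
- **Residual class (3.2.2).** "Non Events are defined as any clinical event that does not meet the criteria of an ACS Event or a Precursor Event". Only one more step is given for this class, namely that its members "will be further classified as either Transient Ischemic Events or as Non Ischemic Events".
- **Forced labels (3.2).** On one side, "any Clinical Event that was not associated with a Type I ST episode detection will be classified as either False Negative or True Negative". On the other, "all Type I ST episodes will be classified as either False Positive or True Positive events".
- **True Negative (3.2.3).** "Absence of a Type I ST episode detection during a Non Event".
- **Use of the labels.** Sensitivity (4.4.1) is True Positives over ACS events only. NPV (4.7.5) is TN / (FN + TN). Deaths otherwise receive a count and a Kaplan-Meier summary (4.7.14).

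**The concern.** Everyone enrolled has documented coronary disease and an ICD indication (3.3.1). In such patients a sudden or unwitnessed death may be a fatal infarction that left no ECG, biomarker or angiographic record. Neither sub-class of Non Event, transient ischemic or non-ischemic, describes an unknown cause. The scheme nevertheless has no other place for such a death once it is treated as a clinical event.

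An unknown outcome is then handled as a known one. For a detection feature, a fatal infarction without an alarm is the most serious kind of miss. Under these rules it would drop out of the primary efficacy denominator and could count in the feature's favour in NPV. The denominator is small, so a few such deaths could matter to the conclusion.

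**Working it through.** **Step 1. Follow a death of undetermined cause with no other ACS criterion through the rules.**

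| Case | Label under 3.2 and 3.2.3 | In the 4.4.1 denominator? |
|---|---|---|
| No alarm; death counts as a clinical event | Non Event, hence True Negative; enters NPV | No |
| No alarm; death does not count as a clinical event | None | No |
| Alarm in the prior 72 h | False Positive, because there is no true ACS Event | No |

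The last column does not depend on how a clinical event is defined. The True Negative label does.

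**Step 2. Check the False Positive label against the safety endpoints.** Sections 4.3.2 and 4.3.3 define a False Positive by the lack of any clinical event within 72 hours of the alarm, not the lack of an ACS event. Read literally, a death that is a clinical event and follows an alarm within 72 hours is a False Positive under 3.2.3 but not under 4.3.2 or 4.3.3. These sections must be reconciled.

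**Step 3. Look for an analysis that covers the gap.** The imputation in 4.3.2 deals with patients lost to follow-up for the safety endpoint. The bootstrap in 4.4.1 reuses the same estimator. The re-analysis in 4.7.15 changes only the time window. None of them varies the status of an undetermined death.

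**Step 4. Size the effect on the primary test.** Inputs: null sensitivity 50% and a Wilson 95% lower bound that must exceed it (4.4.1); at least 41 clinical events at data cut-off (3.1; Protocol 4.5). I take all 41 to be ACS events, which is an assumption because the cut-off says clinical events. The inputs behind 41 and 5,228 are blacked out, so neither figure can be reproduced. That is not a fault of the plan.

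With x detected of n and p = x/n, the lower bound is

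L = [p + z²/(2n) − z·√(p(1−p)/n + z²/(4n²))] / (1 + z²/n), with z = 1.96.

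For 27/41: (0.6585 + 0.0468 − 0.1525) / 1.0937 = 0.505, a pass. For 26/41, L = 0.481, a fail. So 27 is the pass mark.

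Because the Wilson interval inverts the score test, L > 0.5 is the same as (2x − n)/√n > 1.96. This makes the tipping counts easy to check. Adding k missed events keeps x fixed and raises n to 41 + k:

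| Observed | L | Last pass, (2x − n)/√n | First fail, (2x − n)/√n | L at first fail | k to overturn |
|---|---|---|---|---|---|
| 27/41 | 50.5% | 27/41, 2.03 | 27/42, 1.85 | 49.2% | 1 |
| 28/41 | 53.0% | 28/43, 1.98 | 28/44, 1.81 | 48.9% | 3 |
| 29/41 | 55.5% | 29/44, 2.11 | 29/45, 1.94 | 49.8% | 4 |
| 30/41 | 58.1% | 30/46, 2.06 | 30/47, 1.90 | 49.5% | 6 |
| 31/41 | 60.7% | 31/48, 2.02 | 31/49, 1.86 | 49.3% | 8 |
| 33/41 | 66.0% | 33/51, 2.10 | 33/52, 1.94 | 49.9% | 11 |

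**Step 5. Check the other direction.** If the added deaths had an alarm in the prior 72 hours and count as True Positives, sensitivity rises. From 27/41, one such death gives 28/42 (66.7%, L = 51.6%). From a failing 26/41, two give 28/43 (L = 50.2%), a pass. With a mix, 29/41 plus 8 deaths gives L = 49.3% if 2 were alarmed (31/49) and 53.4% if 4 were (33/49).

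**The case against.** Several objections have force.

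- **Clinical event is not defined to include every death.** Section 4.7 lists clinical events and mortality as separate items, and 4.7.8 refers to a definition in the study protocol. A CEC charter or the full investigational protocol, neither in the supplied text, could hold a cause-of-death rule. This stands: the True Negative label is conditional. Exclusion from the sensitivity denominator is not.
- **A fatal event has other routes to ACS.** Any one criterion suffices, and 4.3.1 has the CEC judge whether clinical events relate to ischemia or ACS. This stands, and it limits the point to deaths with no such evidence.
- **Not every such death is an infarction.** These are ICD patients at risk of ventricular arrhythmia. This stands, so counting them all as ACS is conservative and belongs in a supportive analysis.
- **The margin depends on the result.** The pass mark is fragile under any binomial rule; from 33/41 it takes 11 added misses. This stands.

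A reader might infer that an alarmed unexplained death is always a False Positive and so counts against the device on both safety endpoints. The documents do not support that, because 4.3.2 and 4.3.3 use the different wording in step 2. A reader might also infer that sensitivity is biased upward overall. The direction depends on how many of these deaths were alarmed, which is unknown.

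A reader might try to estimate the number of such deaths. Assuming 3% to 8% mortality in 5,228 patients (about 157 to 418 deaths), and 1% to 4% of deaths undetermined and unalarmed, gives 1.6 to 16.7, or about 2 to 17. Neither percentage is in the documents, and 5,228 is an enrolment figure rather than the number who complete Baseline with the feature on. A tenfold range built on assumptions is not evidence that the result would change.

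**Conclusion.** The concern holds in this limited form. In the supplied text, a death the CEC cannot attribute, with no other ACS criterion met, is left out of the primary sensitivity denominator. If it is a clinical event without an alarm, it is credited to NPV as known non-ACS. No planned analysis shows whether this matters.

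The size is a tipping count, not an estimated bias: 1, 3, 4, 6 or 8 added missed events from 27, 28, 29, 30 or 31 of 41. It rests on 41 ACS events, on the deaths concerned being true ACS events, and on none having had an alarm in the prior 72 hours. The NPV effect touches a descriptive measure without a hypothesis. The plan should be changed, but the primary analysis is not invalid.

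**What to change.** 1. Add death of undetermined cause as a CEC class in 3.2.1 and 3.2.2, with an exception to the forced labels in 3.2 so that it is excluded from True Negative and NPV. If a rule already exists in another study document, cite it.
2. Leave the primary sensitivity analysis in 4.4.1 and the False Positive counting for both safety endpoints unchanged. Removing alarmed deaths from False Positives would favour the device against the 15% and 1.9 per patient-year limits. Separately, reconcile the False Positive wording of 3.2.3 with that of 4.3.2 and 4.3.3.
3. Add a supportive analysis to 4.4.1 that counts these deaths as ACS events: True Positive if the device shows a Type I episode in the prior 72 hours, False Negative if not. Report the number of added missed events that would overturn the conclusion.

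The cost is one CEC category and one table; the CEC already reviews all deaths. The supportive estimate may be less favourable than the primary one, and it is conservative because some of these deaths will not be infarctions.

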3.2.3 Classification of Events

True Positive (TP): A Type I ST episode detection that occurs up to 72 hours prior to an ACS Event.

False Positive (FP): A Type I ST episode detection that occurs more than 72 hours prior to an ACS Event or that occurs in the absence of a true ACS Event.

True Negative (TN): Absence of a Type I ST episode detection during a Non Event.

False Negative (FN): Absence of a Type I ST episode detection within 72 hours prior to an ACS Event.

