4.3.2 Primary Safety Endpoint

The ST Monitoring Feature will be evaluated by the percentage of patients with false positive events. The percentage of patients with false positive events is calculated as the number of patients who experience false positives divided by the number of evaluable patients. A False Positive occurs when a clinical event does not occur within 72 hours following a Type I ST episode.

The hypothesis is formally expressed as follows:

H_0 : Percent of patients experiencing a false positive event in 12 months $\geq 15\%$

H_a : Percent of patients experiencing a false positive event in 12 months $< 15\%$

The desired outcome is to reject the null hypothesis at the 2.5% significance level. The null hypothesis will be rejected at the 2.5% significance level if the

Statistical Analysis Plan

upper bound of the 95% confidence interval for the percent of patients experiencing false positive events is less than 15%. The upper confidence bound will be calculated using the Wilson score interval method.

Patient Group

All enrolled patients who have a successful implant or system revision, complete the baseline follow up visit and have the ST Monitoring Feature and Patient Notifier turned ON will be included in the evaluation of this study endpoint. Data collection towards the study endpoint will begin after the Baseline visit.

Further, the analysis population for the primary safety endpoint will be those subjects with the Fortify[®] ST (upgraded), Fortify Assura[®] ST and Ellipse[®] ST. Data from subjects with a Fortify[®] ST device prior to being upgraded will not be included in this analysis.

Analysis

Primary Analysis

The primary analysis will be a complete case analysis where patients who are lost to follow-up before completing their 12 month visit without experiencing a false positive event will be considered non-evaluable and omitted from the analysis of the endpoint. Patients experiencing a false positive event and withdrawing before the 12 month visit will be included in the analysis. The proportion of patients experiencing false positives will be estimated by the number of patients experiencing a false positive event divided by the number of evaluable patients.

Imputation Analysis

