4.3.3 Secondary Safety Endpoint

The ST Monitoring Feature will be evaluated by the False Positive Rate (FPR). The False Positive Rate is calculated as the number of false positives per patient-year of follow-up. A False Positive occurs when there is a Type I ST episode that is not followed by a clinical event within 72 hours. Only ST segment shift events that occur beyond the baseline visit will be included in this analysis.

$$\text{FPR} = \frac{\text{\#of false positive events}}{\text{patient years of follow-up}}$$

The hypothesis is formally expressed as follows:

H₀: Expected FPR ≥ 1.9 per patient-year of follow-up

H_a: Expected FPR < 1.9 per patient-year of follow-up

The desired outcome is to demonstrate that the False Positive Rate is less than 1.9 events per patient-year. The null hypothesis will be rejected at the 2.5% significance level if the 97.5% upper confidence limit (UCL) for the expected FPR is less than 1.9 per patient-year of follow-up.

Statistical Analysis Plan

Patient Group

All enrolled patients who have a successful implant or system revision and have completed the Baseline visit with the ST Monitoring Feature and Patient Notifier programmed ON will be included in this endpoint.

Further, the analysis population for the secondary safety endpoint will be those subjects with the Fortify® ST (upgraded), Fortify Assura® ST and Ellipse® ST devices. The data from subjects with a Fortify® ST prior to being upgraded will not be included in this analysis.

Analysis

Primary Analysis

The expected FPR will be estimated by the observed FPR. To avoid imbalance in the number of false positives that each patient with false positives contributes, the maximum number of false positives from a patient that will be counted toward meeting the requirement on the number of false positives will be two. In addition, for a single follow up period (i.e. one interrogation and device evaluation to the next), if multiple false positive events occur, only one event will be counted toward the analysis. This will prevent multiple false positives that occur before the physician has the opportunity to evaluate the patient and reprogram the device from contributing to an imbalance in the data. For any patients with more than two false positives their follow up time will be truncated to the date of the second false positive.

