4.4 Analysis of Efficacy

4.4.1 Primary Efficacy Endpoint

The efficacy endpoint will be evaluated as the sensitivity of the ST Monitoring Feature to detect clinical events. Sensitivity of the ST Monitoring Feature to detect clinical events will be calculated as the number of True Positive events (as defined in section 3.2.3) divided by the total number of ACS clinical events.

$$\text{Sensitivity} = \frac{\text{\# of TP events}}{\text{Total number of ACS events}}$$

A clinical event is considered to be related to the onset of a Type I ST episode if the clinical event occurs within 72 hours after the onset of a Type I ST episode.

The hypothesis is formally expressed as follows:

H_0 : Sensitivity \leq 50%

H_a : Sensitivity $>$ 50%

The desired outcome is to demonstrate that the sensitivity of the ST Monitoring Feature is greater than 50%. The null hypothesis will be rejected at the 2.5% significance level if the lower bound of the 95% confidence interval for sensitivity is greater than 50%. The lower confidence bound will be calculated using the Wilson score interval method.

Patient Group

All enrolled patients who have a successful implant or system revision, complete the Baseline follow up visit and have the ST Monitoring Feature and Patient Notifier turned ON, and experience clinical events will be included in the evaluation of this study endpoint. Data collection towards the study endpoint will begin after the Baseline visit.

Further, the analysis population for the primary efficacy endpoint will be those subjects with the Fortify[®] ST (upgraded), Fortify Assura[®] ST and Ellipse[®] ST devices. The data from subjects with a Fortify[®] ST prior to being upgraded will not be included in this analysis.

Statistical Analysis Plan

Analysis

Primary Analysis

The expected sensitivity for ST Monitoring Feature will be estimated by the number of true positive events divided by the total number of ACS events.

The 95% confidence limits will be calculated for sensitivity using the Wilson score interval method⁷ for a binomial proportion. The null hypothesis will be rejected if the lower bound of the 95% confidence limit is greater than 50%.

Additional Analysis

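### A Type I detection after the ACS Event time has no class in 3.2.3, counts as a false positive in 4.3.2 and 4.3.3, and turns on an event time that is never defined

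*Protocol*

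**What the plan says.** Protocol 3.2 sets a two-way rule for detections: "all Type I ST episodes will be classified as either False Positive or True Positive events". Section 3.2.3 then defines the classes:

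- True positive: "A Type I ST episode detection that occurs up to 72 hours prior to an ACS Event".
- False positive: a detection earlier than 72 hours before an ACS Event, or one with no true ACS Event at all.
- False negative: "Absence of a Type I ST episode detection within 72 hours prior to an ACS Event".

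The endpoint sections restate the rule differently. Section 4.3.2 (primary safety): "A False Positive occurs when a clinical event does not occur within 72 hours following a Type I ST episode". Section 4.3.3 (secondary safety): "A False Positive occurs when there is a Type I ST episode that is not followed by a clinical event within 72 hours". Section 4.4.1 (primary efficacy) links an event to an episode "if the clinical event occurs within 72 hours after the onset of a Type I ST episode" and computes sensitivity as the "number of True Positive events (as defined in section 3.2.3) divided by the total number of ACS clinical events".

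Section 4.7.4 defines PPV with all Type I episodes as the denominator and equates that total with true plus false positives. Section 4.7.15 repeats the endpoints with a 14-day window but adds no rule for detections after the event. The SAP carries the same wording in the same sections.

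**The concern.** The feature detects ST shifts, and the ACS definition in 3.2.2 includes ST elevation infarction and new ST depression or elevation. An alarm while the event is under way is a foreseeable way for the device to work, yet 3.2.3 looks only backwards from the event. Such an alarm can be unclassified in one section and a false positive in another, while the event that it detected counts as missed.

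The line between a true positive and this outcome is the time of the ACS Event, which the documents do not fix. It could be symptom onset, presentation, ECG, biomarker, angiography or PCI. If it stays open, it can be settled after the detections are known, in a trial whose efficacy result may rest on about 41 events.

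**Working it through.** **1. Apply each rule to one case.** Take a Type I detection strictly after the ACS Event time, with no detection in the 72 hours before the event and no other clinical event in the 72 hours after the detection.

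| Rule | Result |
|---|---|
| 3.2 | Must be a true or a false positive |
| 3.2.3 true positive | No: the detection is not before the event |
| 3.2.3 false positive | No: it is not more than 72 h before an ACS Event, and a true ACS Event did occur |
| 3.2.3 false negative | Yes, for the ACS event |
| 4.3.2 and 4.3.3 false positive | Yes: no clinical event follows |
| 4.4.1 association | Not related: the event came before the episode |

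Both conditions matter. With an earlier detection inside 72 hours, the ACS event is not a false negative. With a later clinical event inside 72 hours, the detection is not a false positive under 4.3.2 and 4.3.3.

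**2. Event time.** Section 3.2.2 lists criteria that become known at different times, such as a biomarker, a new Q-wave, angiography or a revascularization. If the event is dated by angiography, an alarm after symptoms but before angiography is a true positive. If it is dated by symptoms, the same alarm has no class.

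**3. Which later event counts.** Section 3.2.3 refers to ACS Events. Sections 4.3.2 and 4.3.3 refer to clinical events, which under 3.2.1 and 3.2.2 include Non Events. An episode followed within 72 hours only by a Non Event is a false positive under 3.2.3 but not under 4.3.2 or 4.3.3.

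**4. PPV.** Let L be the number of late detections. Under 3.2.3, TP + FP = all Type I episodes − L, so the two descriptions of the denominator in 4.7.4 differ by L.

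**5. Size for sensitivity.** The stated minimum is 41 clinical events (4.5), taken here as ACS events. That figure cannot be reproduced because the assumed sensitivity and power are redacted. Back-solving gives 80% exact power at a sensitivity of 0.706 and 90% at 0.736, so 41 is plausible.

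The Wilson lower bound, with z = 1.96 and n = 41, is [p + z²/(2n) − z√(p(1−p)/n + z²/(4n²))] / (1 + z²/n). Here z²/(2n) = 0.0468 and 1 + z²/n = 1.0937.

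- 27/41: (0.6585 + 0.0468 − 0.1525)/1.0937 = 50.5%, passes.
- 26/41: (0.6341 + 0.0468 − 0.1547)/1.0937 = 48.1%, fails.
- 30/41: (0.7317 + 0.0468 − 0.1435)/1.0937 = 58.1%, passes.

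One event is 1/41 = 2.4 points. If 30 of 41 events are detected in total and 4 of them only after the event time, the pre-event count is 26/41, which fails, and the count with in-event detections is 30/41, which passes.

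**6. Size for primary safety.** As a ceiling, suppose that all 41 events are in different patients, each adding a false-positive patient who would not otherwise have been one, and that all 5,228 patients are evaluable: 41/5,228 = 0.78 points. With 80% evaluable (an assumption), 41/4,182 = 0.98 points. The largest count that still meets the 15% goal is 733/5,228 = 14.0%.

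**The case against.** Counting only detections before the event is a defensible, conservative choice for an alerting feature. That stands, and the primary estimator should not change. A reader could also stretch the absence clause in 3.2.3 to mean that no ACS Event follows. That closes the gap, but only by calling a real in-event detection a false alarm.

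The event time may be set in the separate investigational protocol, to which 4.7.8 and 4.7.10 refer. That is possible, but it is not in the documents reviewed here. The wording of 4.3.2 and 4.3.3 may be loose, since 4.4.1 speaks of clinical events and then divides by ACS events. That too is possible, and one definition would settle it.

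Four stronger readings are tempting, and the documents do not support them:

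- *A detection exactly at the event time is also excluded.* Both 3.2.3 and 4.4.1 can be read to include zero hours, so a true positive is a fair reading.
- *Every alarm after symptom onset is penalised.* The documents do not tie the event to symptom onset, and the false-positive and false-negative labels each carry a condition.
- *PPV changes with the section used.* True positives come from 3.2.3, and the stated denominator holds every episode. The fault is the mismatch inside 4.7.4.
- *The trial loses power.* At an assumed sensitivity of 70%, exact power at 41 events is 78%, and it falls to 53% or 29% if 2 or 4 events are detected only late. But the 70% is an assumption. If the redacted planning value was already a pre-event sensitivity, as the 3.2.3 estimator implies, those events were already counted as misses.

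**Conclusion.** The point holds for detections strictly after the ACS Event time. Sections 3.2 and 3.2.3 contradict each other on them, 4.3.2 and 4.3.3 make them false positives unless another clinical event follows within 72 hours, and the event time that decides the matter is undefined. The mismatch between clinical events and ACS Events, and the PPV denominator, belong to the same repair.

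The importance is modest. At 41 events each late-only detection is 2.4 points of sensitivity, but with the pre-event primary estimator kept, this shows only in a supportive analysis. The effect on the primary safety endpoint is at most about 0.8 points, given 41 ACS events and all 5,228 patients evaluable; it grows if there are more events or fewer evaluable patients. That ceiling covers late detections only. The documents give neither the number of late detections nor the number of episodes followed only by a Non Event, so neither effect can be estimated.

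**What to change.** - In 3.2.3, define the ACS Event time stamp, to be set by the CEC blinded to device detections. Section 3.2.1 specifies blinding to patient and site information only.
- Add a class for detection during an ACS event, with a fixed post-event window, and state how a detection at the event time itself is classed. Amend the two-way rule in 3.2 to match.
- Use one false-positive definition, tied to ACS Events and excluding the new class, in 3.2.3, 4.3.2, 4.3.3 and 4.7.4.
- Report PPV with and without the new class in the denominator.
- Keep the primary sensitivity as pre-event detections only. Pre-specify one supportive sensitivity that counts in-event detections as true positives.

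The cost is SAP wording, one more category and one more table. Excluding the new class makes the false-positive figures slightly more favourable to the device, which is why PPV should be shown both ways. Tying the definition to ACS Events works in the other direction, because episodes followed only by a Non Event then count as false positives in the safety endpoints.
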